4.2. Scientific Rationale for Study Design

4.2.1. Cohort Design

This study will enroll subjects into 4 cohorts (the Broad Panel Cohort, the Exploratory Cohort, the Cholangiocarcinoma Expansion Cohort, and the Pediatric Cohort). The histology agnostic Broad Panel Cohort will enroll subjects \geq 12 years of age with target FGFR mutations or any FGFR gene fusion. The Exploratory Cohort will enroll subjects with FGFR mutations not captured in the Broad Panel Cohort. A separate Cholangiocarcinoma Expansion Cohort will enroll subjects with target FGFR mutations or any FGFR gene fusion once the Broad Panel Cohort has reached the cap of approximately 30 subjects for cholangiocarcinoma. The definition of target FGFR mutations and rationale for the cohort design are outlined below. The Pediatric Cohort will enroll subjects \geq 6 to <18 years of age with FGFR mutations, any FGFR gene fusion, or FGFR internal tandem duplication. Adolescent subjects enrolled in the Broad Panel Cohort (\geq 12 to <18 years) will be analyzed as part of the Broad Panel Cohort and the Pediatric Cohort.

Over 8,000 unique mutations in FGFR1-4 have been reported in the GENIE (the AACR Project Genomics Evidence Neoplasia Information Exchange) and FoundationInsights[™] genomic databases as of February and May 2019, respectively. It is possible that many of these mutations represent passenger events and may not be drivers of disease. To identify FGFR mutations with oncogenic driver potential and sensitivity to erdafitinib, genomic filtering and in-vitro sensitivity assays were applied to FGFR mutations in the GENIE and FoundationInsights databases.

The GENIE database represents ~46,000 patients across 48 cancers, and the FoundationInsights database contains genomic data from ~231,000 patients from 64 cancers. The >8,000 unique mutations in FGFR1-4 were collected and annotated for pathogenicity based on the following criteria:

- Presence of the variant in 1 of 2 oncology variant knowledge databases, which annotate the oncogenic effect of somatic molecular alterations (OncoKB 2019, Chakravarty 2017, Cancer Hotspots 2019, Chang 2018)
- Annotation of the variant in Foundation Insights genomic database indicating known or likely pathogenicity
- Variant recurrently detected in the GENIE genomic database (GENIE 2019)
- Variant recurrently detected in the FoundationInsights genomic database (FoundationInsights 2019)
- Variant identified in multiple tumor types across genomic datasets
- Variant is not in a position of a canonical gatekeeper mutation (FGFR1_V561, FGFR2_V564, FGFR2_N549; FGFR3_V555, FGFR4_V550)

The resulting list of FGFR mutations were subsequently tested in transient transfection assays for in-vitro sensitivity to erdafitinib, determined by inhibition of extracellular-signal-regulated kinase (ERK) phosphorylation. FGFR mutations meeting the above criteria and with in-vitro sensitivity to erdafitinib were designated as target FGFR mutations. The list of Target FGFR Mutations also includes additional mutations with clinical or correlative evidence supporting inclusion. The List of Target FGFR Mutations is provided in Section 10.11.

The frequency of target FGFR alterations in Table 1 includes filtering for likely pathogenic FGFR gene fusions based on assessment of fusion characteristics and recurrence. Molecular eligibility for this study has been extended to subjects with any FGFR gene fusion (FGFR gene fusions must have an intact FGFR kinase domain. FGFR gene identifiers for reference are provided in Section 5.1 Criterion 2). This extension of molecular ability is based on clinical experience in cholangiocarcinoma and other tumor types where clinical responses to erdafitinib were observed in patients with novel gene fusions.

A subgroup of subjects in the Broad Panel Cohort with a defined panel of pre-specified FGFR markers will be identified as the Core Panel Cohort (see Section 9.3.1). The Core Panel Cohort will be used only for statistical analysis purposes and will not affect enrollment. FGFR markers for the Core Panel Cohort were selected based on observed clinical activity in previous studies or a high level of recurrence of these alterations across tumor histologies.

The selection process described above, while aiming to increase the likelihood of evaluating erdafitinib activity in FGFR-driven tumors, is not expected to capture all FGFR mutations with oncogenic driver potential or sensitivity to erdafitinib. Therefore, the Exploratory Cohort has been included to capture and assess driver mutation potential and sensitivity in FGFR mutations not eligible for the Broad Panel Cohort.

Subjects from all solid tumor histologies (except bladder) with an FGFR mutation or fusion identified via local testing results (as outlined in Section 8.1.1.1) are considered molecularly eligible for the study, pending review and approval by the sponsor. However central molecular screening will be selective to specified tumor histologies. Based on the predicted frequency of target FGFR alterations, prevalence of tumor histology, and predictive modeling of distribution; the tumor histologies that were selected for central molecular screening in this study are provided in Figure 6.

4.2.2. Biomarker Collection

Biomarker samples will be collected to evaluate the mechanism of action of erdafitinib and may help to identify population subgroups that respond differently to erdafitinib. The goal of the biomarker analyses is to further understand the mechanism of action and potential erdafitinib-clinical response relationships. Biomarker samples may be used to help address emerging issues and to enable the development of safer, more effective, and ultimately individualized therapies.

4.2.3. Patient-reported Outcomes Research

Patient-reported outcome data complement data collected by other methods to support the clinical data and cost-effectiveness modeling as well as contributing to enhanced communication of value to patients, clinicians, regulators, and payers. The patient-reported outcome (PRO) endpoints of interest include domain scales from the EORTC-QLQ-C30 (for subjects ≥ 18 years of age) or Peds FACT-Br (for subjects < 18 years of age), PGIS, PGIC, and EQ-5D-5L (utility value and visual analog scale). PRO assessments are necessary to quantify patient benefit early in the development on an investigational drug. Collecting PRO assessments at this time will support further development in future studies. PRO data will be collected as outlined in the Schedule of Activities to understand how the endpoints change over time.

4.2.4. Study-Specific Ethical Design Considerations

Potential subjects will be fully informed of the risks and requirements of the study and, during the study, subjects will be given any new information that may affect their decision to continue participation. They will be told that their consent to participate in the study is voluntary and may be withdrawn at any time with no reason given and without penalty or loss of benefits to which they would otherwise be entitled. Only subjects (or their legally acceptable representative) who are fully able to understand the risks, benefits, and potential adverse events of the study, and provide their consent voluntarily will be enrolled.

When referring to the signing of the informed consent/assent form (ICF), the terms legal guardian and legally acceptable representative refer to the legally appointed guardian of the child with authority to authorize participation in research. For each subject, his or her parent(s) (preferably both parents, if available) or legally acceptable representative(s), as required by local regulations, must give written consent (permission) according to local requirements after the nature of the study has been fully explained and before the performance of any study-related assessments. Assent must be obtained from children (minors) capable of understanding the nature of the study, typically subjects 7 years of age and older, depending on the institutional policies; children ≥ 6 to <12 years of age, adolescents 12 years of age and above and adults will be enrolled in this study. Minors who reach the age of majority (per local regulations) during study will need to (re)sign an ICF. For the purposes of this study, all references to subjects who have provided consent (and assent as applicable) refers to the subjects and his or her parent(s) or the subject's legal guardian(s) or legally acceptable representative(s) who have provided consent according to this process. Minors who assent to a study and later withdraw that assent should not be maintained in the study against their will, even if their parent(s) still want them to participate.

In view of the positive results for the subjects with urothelial cancer and select FGFR alterations in these studies and the prognosis for the subject population being considered for the study, a positive risk-benefit profile is anticipated. It should be noted that in the Phase 1 study, different histologies harboring FGFR amplifications, mutations or translocations did not behave uniformly to erdafitinib treatment. Instead the response was higher in certain tumor histologies such as urothelial cancer or cholangiocarcinoma compared to other tumor histologies included in the study. Subjects will be closely monitored throughout the study, as discussed throughout this protocol, for

both safety and clinical benefit.

The potential risks of erdafitinib to adults, as well as children and adolescents, include central serous retinopathy and hyperphosphatemia. Pre-clinical findings of cartilage dysplasia could be indicative of possible bone growth abnormalities in children and adolescents. The safety profile of erdafitinib, based on the urothelial population, was characterized by mild to moderate eye, skin and nail disorders; these events were manageable with available medical measures, temporary treatment interruption, or eventual dose reduction.

The total blood volume (approximately 230 mL for adults and 275 mL for adolescents over 6 cycles, including the screening and end of study visits [approximately 15 mL is collected at each additional cycle]) that will be collected is considered within the normal range allowed for this subject population over this time frame, including the adolescent subjects. For adult subjects, the amount of blood collected is less than the American Red Cross standard blood donation of 500 mL over 60 days (American Red Cross 2019). For children and adolescents, generally no more than 1 percent of the total blood volume may be collected at any one draw or over a 24-hour period, and no more than 3 percent of the total blood volume may be collected over a 30-day period (Veal 2014, Howie 2011, EMA 2019). Thus, an adolescent weighing 40 kg would have a total blood volume of 3.2 liters and a limit of approximately 30 mL at any 1 blood draw and 90 mL over 30 days. In this study, the total blood volume collected from an adolescent subject weighing 40 kg exceeds the 30 mL limit at Cycle 1 Day 1 visit only, due to the collection of a 20 mL blood sample for circulating tumor DNA. All subsequent study visits do not collect blood volumes in excess of 30 mL. This difference from the maximum limit increases as body weight decreases. The investigator should evaluate the risk versus the potential benefit of enrolling an adolescent subject with lower body weights into this study.

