Taking into account the measures utilized to minimize risk to subjects in this study (eg, guidance regarding blood volume in adolescents in Section 4.2.4, guidance for specific erdafitinib toxicities in Section 6.6.1, prohibited medications in Section 6.5.2, precautions for concomitant medications in Section 6.5.3, and monitoring of results of safety assessments in Section 8.3), the potential risks identified in association with erdafitinib are justified by the anticipated benefits that may be afforded to patients with advanced solid tumors with FGFR gene alterations for whom there are no available treatments, including subjects ≥ 6 years of age. More detailed information about the known and expected benefits and risks of erdafitinib may be found in the Investigator's Brochure.

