8. STUDY ASSESSMENTS AND PROCEDURES

Overview

The Schedule of Activities (Section 1.3 for Adults and Section 1.4 for Children and Adolescents) summarizes the frequency and timing of safety, efficacy, PK, biomarker, and other measurements applicable to this study. Patient-reported outcome questionnaires should be completed before any other assessments at each clinic visit.

The number of samples and the blood volume will vary depending on the number of cycles of the study drug that the subject receives. The total blood volume to be collected from each subject will be approximately 230 mL for adults and 275 mL for children and adolescents over 6 cycles (including the screening and end of study visits, approximately 15 mL is collected at each additional cycle). (See Section 4.2.4 for additional information regarding the blood volume). Unscheduled blood samples may be required for safety issues of individual subjects.

Study-Specific Materials

The investigator will be provided with the following supplies:

- Erdafitinib Investigator's Brochure
- Pharmacy manual/study site Investigational Product Manual and the Investigational Product Preparation Instructions
- Laboratory manual
- National Cancer Institute Common Terminology Criteria for Adverse Events (NCI-CTCAE) Version 5 or higher

- PRO completion guidelines
- Imaging Guidelines
- IWRS Manual
- Electronic data capture (eDC) Manual
- eSource Manual
- Sample ICFs

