8.2.1.1. RECIST and RANO Assessment of Disease; References	Updated RANO references (Wen 2010 and van den Bent 2011), including assessment criteria for both low- and high- grade gliomas	To provide assessment reference for low- and high- grade gliomas

Section Number and Name	Description of Change	Brief Rationale
1.3. Schedule of Activities for Adults; 1.4. Schedule of Activities for Adolescents; 8.2. Efficacy Assessments; 8.2.1.2. Radiographic Assessment	Added skin lesion photography as an efficacy assessment as applicable	To allow for photography assessments when radiological assessment is not feasible
Synopsis; 1.4. Schedule of Activities for Adolescents; 3. Objectives; 8.5. Pharmacokinetics;	Added serial PK samples for adolescents on Cycle 3, Day 1 and Cycle 4 Day 1; deleted samples on Cycle 2, Day 1	To fully characterize the PK profile in adolescents
9.4.4. Pharmacokinetics, 9.4.4. Pharmacokinetic and Pharmacodynamic Analyses	Moved protein binding sample to Cycle 3, Day 1 (previously Cycle 2, Day 1)	To align with PK sampling
	Updated the PK endpoints to indicate both adults and pediatric subjects; removed population PK analysis from the secondary endpoint	To remove a secondary endpoint linked to an optional analysis (population PK)
1.3. Schedule of Activities	Changed fresh tumor biopsy assessment to read as optional (previously 'where clinically feasible'); specified sampling at the time of disease progression (previously end of treatment)	To clarify that fresh tumor biopsy is optional and timepoint for sampling
Figure 2	Added a footnote that the Exploratory Cohort is closed for enrollment	To indicate that the Exploratory Cohort enrollment is completed
4.2.4. Study-Specific Ethical Design Considerations	Updated total blood volume collected for adolescents on Cycle 1 Day 1 visit	To indicate that collection exceeds the maximum 30 mL on Cycle 1 Day 1
4.3. Justification for Dose	Updated for flow and to strengthen justification for adult dosing	Updated for flow and to strengthen justification for adult dosing
5.3. Lifestyle Considerations	The following was added: Male and female subjects should be advised on sperm banking and egg preservation, respectively, prior to entering the study, if appropriate.	To address a request from a regulatory authority in the clinical program
6.5.1. Permitted Medications	Added that surgery or biopsy of target lesions is not permitted	To prohibit surgery or biopsy of target lesions

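### Section 4.2.4 works its 1% blood-volume limit only for a 40 kg adolescent, although children from age 6 share the Schedule; Cycle 1 Day 1 drawn in one day exceeds 1% up to 37.5 kg, and the 20 mL ctDNA sample alone exceeds it below 25 kg

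*Protocol*

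**What the plan says.** Protocol Section 4.2.4 states a general limit for pediatric subjects: "no more than 1 percent of the total blood volume may be collected at any one draw or over a 24-hour period". A second limit is 3% over 30 days. The only worked case is a 40 kg adolescent with 3.2 L of blood, giving about 30 mL per draw and 90 mL per 30 days. In that subject the volume "exceeds the 30 mL limit at Cycle 1 Day 1 visit only, due to the collection of a 20 mL blood sample"; the sample in question is ctDNA. The section adds that the departure from the limit widens at lower weights. It then reassures: "All subsequent study visits do not collect blood volumes in excess of 30 mL". Its advice for light subjects is: "The investigator should evaluate the risk versus the potential benefit of enrolling an adolescent subject with lower body weights into this study". It describes the six-cycle total as "considered within the normal range allowed for this subject population over this time frame, including the adolescent subjects".

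Section 8 gives that total as "approximately 230 mL for adults and 275 mL for children and adolescents over 6 cycles", so children are on the adolescent volume. Section 1.4 is a single Schedule for ages 6 to under 18. Section 2.3 lists "guidance regarding blood volume in adolescents in Section 4.2.4" among the measures that justify the risk, including for subjects from age 6.

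Three other provisions bear on the point:
- The pediatric Schedule takes ctDNA at Cycle 1 Day 1, Cycle 4 Day 1, Cycle 7 Day 1 and end of treatment. The synopsis and Section 3 treat this work as exploratory.
- Hematology, chemistry and parathyroid hormone may be drawn up to 3 days before Day 1 of a cycle.
- A footnote on the PK and biomarker block lets an investigator who sees a risk in any blood collection ask the sponsor about postponing samples or taking fewer tubes.

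**The concern.** The limit is stated for children and adolescents, but the only weight at which it is tested is 40 kg. A permitted volume that scales with weight shrinks quickly for a young child, while the scheduled volume stays the same. The 30 mL reassurance and the normal-range statement are therefore not shown to hold for the lightest subjects the trial admits, and the advice on low weight does not mention children.

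The amendment history suggests how this arose. Amendment 2 revised the Cycle 1 Day 1 statement, with the reason "To indicate that collection exceeds the maximum 30 mL on Cycle 1 Day 1". Amendment 3 then lowered the entry age from 12 to 6. The current section contains no weight below 40 kg. The history is used here only to date the text; the gap is in the current wording.

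At stake is a site that follows the Schedule in a light child and exceeds the protocol's stated pediatric guideline because of a sample that serves only an exploratory objective.

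**Working it through.** **Inputs (Protocol 4.2.4 unless noted)**
- Limit: 1% of total blood volume per draw or 24 h.
- Blood volume: 3.2 L at 40 kg.
- Cycle 1 Day 1 volume: more than 30 mL; the exact total is not given.
- ctDNA sample: 20 mL, stated for an adolescent. Assumed the same in children because Section 8 gives both groups one total.

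**Step 1. Reproduce the plan's figures.** 3200 / 40 = 80 mL/kg. 1% of 3200 = 32 mL (stated as about 30). 3% of 3200 = 96 mL (stated as 90, three times the rounded 30). These agree once rounding down is allowed for.

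**Step 2. Limit per kg.** 0.01 × 80 = 0.8 mL/kg.

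**Step 3. Threshold weight = volume / 0.8.**
- All Cycle 1 Day 1 blood in one day: 30 / 0.8 = 37.5 kg. Since the volume is above 30 mL, 1% is exceeded at every weight up to and including 37.5 kg, and the true cut-off lies higher.
- ctDNA alone: 20 / 0.8 = 25 kg. This holds even if all other blood is moved to another day.

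**Step 4. By weight.**

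| Weight (kg) | 1% limit (mL) | 30 mL as % of blood volume | 20 mL as % of blood volume |
|---|---|---|---|
| 20 | 16 | 1.88 | 1.25 |
| 25 | 20 | 1.50 | 1.00 |
| 30 | 24 | 1.25 | 0.83 |
| 37.5 | 30 | 1.00 | 0.67 |
| 40 | 32 | 0.94 | 0.63 |

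The 30 mL column understates Cycle 1 Day 1, which is above 30 mL.

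**Step 5. Sensitivity.** With the plan's rounded limit (30 mL at 40 kg, or 0.75 mL/kg) the thresholds are 30 / 0.75 = 40 kg and 20 / 0.75 = 26.7 kg. If blood volume is assumed to be 70 to 80 mL/kg, they are 37.5 to 42.9 kg and 25 to 28.6 kg.

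**Step 6. Effect of the 3-day window.** If the safety panel is drawn on an earlier day, Cycle 1 Day 1 falls to the 20 mL ctDNA sample, which fits 1% from 25 kg. Below 25 kg the window does not help.

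**Step 7. Later visits.** A ceiling of 30 mL demonstrates compliance with 1% only from 30 / 0.8 = 37.5 kg. For lighter children compliance is not shown either way.

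**The case against.** There is a fair case on the other side, and parts of it stand.

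- **The trend is disclosed.** Section 4.2.4 says the excess grows as weight falls. That is true, but it gives no figure below 40 kg, and the action it asks for is an enrollment judgment about adolescents.
- **Sites have a route.** The footnote covers ages 6 to under 18 and sits on the block that contains ctDNA. It tempers the severity. It still depends on the investigator perceiving a risk, sets no weight or volume, and is not referred to in Section 4.2.4.
- **One-day collection is permitted, not required.** This stands, and the 37.5 kg figure is conditional on it. The 25 kg figure is not.
- **The limit is a general one.** The text says generally, so exceeding it departs from stated guidance and does not break an absolute rule.
- **The 20 mL volume in children is inferred.** It appears only in a sentence about a 40 kg adolescent. Neither the pediatric ctDNA row nor Section 8.6 gives a volume.

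A reader might also infer that the protocol contains an arithmetic error. It does not: its figures reproduce, and what is missing is their extension to lighter subjects.

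A reader might further infer that the 3% limit is breached, or that cutting ctDNA would secure it. The documents support neither. Safety-panel volumes are not given, and the limit applies to any 30-day period. Days 14 to 43 contain five panel visits (Cycle 1 Day 14, Cycle 2 Days 1, 7 and 14, and Cycle 3 Day 1) and the serial PK profile, but no ctDNA. Reducing ctDNA cannot help in that window.

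**Conclusion.** The point holds for the 1% limit. At 80 mL/kg, Cycle 1 Day 1 collected in one day exceeds 1% at any weight up to 37.5 kg. The ctDNA sample alone exceeds it below 25 kg, reaching 1.25% at 20 kg. The current text neither works the limit for such children nor tells sites what to do.

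This rests on the protocol's implied blood volume per kg, on same-day collection for the 37.5 kg figure, and on 20 mL also being drawn in children. Confidence is high for the arithmetic and moderate for that last assumption. The documents give no weights for enrolled children, so nothing here says how many are affected or that any was harmed. Compliance with the 3% limit is unknown. Severity is minor to moderate.

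**What to change.** 1. **Pediatric Schedule and laboratory manual.** Limit ctDNA so that the day's total stays within 0.8 mL/kg. Below 25 kg, take at most 0.8 mL/kg of ctDNA (16 mL at 20 kg, with nothing else drawn that day) or omit it. Where the Cycle 1 Day 1 total does not fit, tell sites to draw the safety panel on an earlier day within the existing 3-day window or to reduce ctDNA.

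2. **Sections 4.2.4 and 2.3.** Restate the limit for lighter weights, for example 20, 25 and 30 kg, using actual per-visit volumes. Confine the normal-range and 30 mL assurances to weights where they hold. Extend the low-weight advice to children and cross-reference the Schedule footnote.

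3. **Checks for the sponsor, using actual tube volumes.** Test the 3% limit over every rolling 30-day window, including Days 14 to 43. Test the Cycle 3 Day 1 total against 1%. On that day six PK samples and one protein-binding sample are scheduled. If the 2 mL in Section 8.5 is per sample, they take 6 × 2 + 1 to 4 = 13 to 16 mL before any panel, against 16 mL allowed at 20 kg. If 2 mL covers the whole visit, they take 2 + 1 to 4 = 3 to 6 mL.

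The cost is wording in the protocol and laboratory manual, smaller or missing exploratory ctDNA samples in small children, and sometimes an extra venipuncture when the panel is drawn before Day 1. The ctDNA limit removes no safety test.
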